10.2. Reporting Procedures for Serious Adverse Events

A serious adverse event (SAE) occurring to a participant will be reported to the REC that gave a favourable opinion of the study where in the opinion of the Chief Investigator the event was 'related' (resulted from administration of any of the research procedures) and 'unexpected' in relation to those procedures. Reports of related and unexpected SAEs should be submitted within 15 working days of the Chief Investigator becoming aware of the event, using the HRA report of serious adverse event form (see HRA website). Any SAEs that are continuing at trial withdrawal or 26-week follow-up completion will be marked as "Continuing" at the end of the study.

10.3. Other Adverse Events

We will record incidences of falls, accidents (road-traffic accidents and work-related injuries), near miss driving incidents, and falling asleep while driving alongside outcomes at baseline, 4-, 8-, and 26-weeks post-randomisation. We will also assess proportion of each group showing an increase in suicidal ideation using item 9 from the PHQ9. As above, these outcomes will be assessed at baseline, 4-, 8-, and 26-weeks post-randomisation.

11. STATISTICS AND ANALYSIS

11.1. Statistical Analysis Plan (SAP)

Analyses will be described in detail in a Statistical Analysis Plan (SAP). All analyses will be conducted in accordance with PC-CTU SOPs. Our main planned analyses are summarised below.

11.2. Description of the Statistical Methods

In accordance with CONSORT guidelines, we will record and report participant flow. Descriptive statistics of recruitment, drop-out, and completeness of interventions will be provided. The primary analysis will be according to randomised treatment assignment and will include all randomised participants for whom data are available, as defined by protocol eligibility. Baseline variables will be presented by randomised group using frequencies (with percentages) for binary and categorical variables and means (and standard deviations) or medians (with lower and upper quartiles) for continuous variables. There will be no tests of statistical significance nor confidence intervals for differences between groups on any baseline variables. The results from the trial will be presented as comparative summary statistics (difference in proportions or means) with 95% confidence intervals. All tests will be done at a 5% two-sided significance level. The study results will be reported in accordance with the CONSORT 2010 statements and a full detailed statistical analysis plan will be prepared before recruitment starts.

The primary comparison is the mean difference in the primary outcome (PHQ-9 score) at 26 weeks for all randomised participants, as defined by protocol eligibility criteria, regardless of what intervention they actually received or compliance of intervention. A multi-level model will be fitted to the data with PHQ-9 score at 4-, 8- and 26-weeks post-randomisation, adjusting for minimisation factors and baseline score. Practice and participant will be included as random effect and an interaction term for the treatment by time interaction will allow the treatment effect to differ at each time point. "Therapist effect" (i.e. effect from the intervention being delivered by the same nurse) will also be considered in the model. A similar approach will be used for secondary (mechanistic) outcomes. Numbers of participants who experienced serious adverse events will be compared in the safety population using Chi-square or Fisher's exact test. Pre-specified subgroup analyses of the primary outcome will be explored by baseline depression severity, insomnia severity, and antidepressant medication use at baseline.

Causal mediation analysis with bootstrap confidence intervals will be carried out to estimate the indirect effect of treatment on depression at 26 weeks via insomnia (ISI) at 4 weeks. We will use measures collected at all time-points to estimate the direct and indirect effects in the presence of missing data and accounting for measurement error (29). This approach uses structural equation modelling to estimate the "true" value of the mediator accounting for measurement error using a latent variable by assuming the variance of the measurement error is constant across all time points. All measures of the mediator will be included in the

model, but the 4-week measure will be used as the main mediator of interest. The model will also adjust for baseline values of mediator and outcome to account for possible confounding. Full information maximum likelihood will be used to estimate the model, as this is valid under a missing at random (MAR) assumption; that is, missingness is dependent only on variables included in the analysis model. If there are non-identifiability issues, then the indirect effect will be estimated using an approach similar to Baron and Kenny but will follow the adaptation in Freeman et al. (30) which makes use of linear mixed effects models. This is valid under a MAR assumption but does not account for measurement error in the mediator. We will use the same approach to examine whether change in mechanistic outcomes (at 8 weeks) mediates change in depressive symptoms (at 26 weeks).

11.3. Sample Size Determination

We have powered our trial based on a minimum between-group standardised effect size difference (SMD) of 0.50, reflecting approximately a 3-point difference between arms (pooled SD=6) on the primary outcome, PHQ-9. There is preliminary evidence of large effect size differences following sleep treatment in depression, but these studies have mainly been pilot RCTs, recruiting very small sample sizes (31-33). Our medium effect size estimate is informed by 1) our meta-analysis of SRT on depressive symptoms; 2) our previous studies investigating the effects of CBT for insomnia on PHQ-9 scores in community-recruited participants (34, 35); 3) the minimum effect size that we would consider clinically important; and 4) a realistic treatment effect on depressive symptoms when adding a targeted sleep treatment to ongoing TAU for depression.

Assuming a SMD of 0.50 with power set at 90%, significance level at 5%, and accounting for up to 20% attrition (36, 37), a sample size of 250 participants (135 in the SRT group and 115 in the control group) is required to detect effects on the primary depression outcome at 26 weeks. The sample size also accounts for the "therapist effect", assuming an intraclass correlation coefficient of 0.01 and a cluster size of 40. In terms of the mediation hypothesis, this sample size will have more than 90% power to detect a small-to-medium effect for the indirect path through insomnia severity (standardised coefficients for A and B paths = 0.3, giving an indirect effect of 0.09). This sample size will also enable detection of medium effect sizes for our mechanistic outcomes, which we consider plausible based on studies showing medium-to-large effects on our selected measures following either depression treatment or sleep treatment (e.g. SMD=0.60 for actigraphy-defined sleep efficiency (38); SMD=0.62 for PTQ (39); SMD=1.02 for FERT(17)).

11.4. Analysis populations

The primary analysis population will be all randomised participants, as defined by protocol eligibility criteria, regardless of what intervention they actually received, compliance of intervention, or completion of outcome. We will also perform exploratory Compiler Average Causal Effect (CACE) analysis to assess the effects of minimum treatment compliance (defined as attending at least 3 treatment sessions) and full treatment compliance (attending all 6 treatment sessions) on the primary outcome.

The safety population will consist of participants who engaged to some extent (defined as attending at least one session of SRT), according to the treatment they actually received (as-treated).

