9.5. Blinding and codebreaking

The study is an open label trial. The participants and nurses will know the treatment allocation due to the design of the study. Treatment providers (i.e. nurses delivering SRT) will not be involved in the collection of trial outcomes. Outcomes (questionnaires, actigraphy, computer tasks) will be self-completed, limiting the possibility of observer/interviewer bias. Communication from the research team to participants, post-randomisation, will be limited to collection of outcome assessments and not therapeutic procedures. Should participants want to complete questionnaire outcomes over the phone, we will ensure that the researcher is blind to group allocation. Actigraphy data will be scored by a researcher who will be blind to group allocation.

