9.10. Early Discontinuation/Withdrawal of Participants

Each participant has the right to withdraw from the trial at any time, without the need to provide a reason and in knowledge of the fact that withdrawing from the trial will not affect their future care from their healthcare provider. However, de-identified data that have already been collected and incorporated in the study database will be included in the analysis (and any personally identifiable data will be destroyed). In addition, the Investigator may discontinue a participant from the trial (or intervention) at any time if the Investigator considers it necessary for any reason including, but not limited to:

- Ineligibility (either arising during the trial or retrospectively)
- For safety reasons, rendering participation in the trial or intervention inappropriate

In the event of an investigator withdrawal, the reason will be recorded on the eCRF.

A participant may wish to discontinue their treatment and/or withdraw from follow-up data collection. If a participant wishes to discontinue their treatment, the study team will contact the participant and ask if they are still willing to participate in the collection of follow-up data. Participants that continue to participate in follow-up data collection will not be considered a withdrawal. If a participant wishes to withdraw from follow-up data collection, data collected up to the point of withdrawal will still be used, as detailed in the PIS.

The reason for withdrawal, if provided, will be recorded on the eCRF.

No participants will be replaced if they are discontinued or withdraw.

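### Section 9.10 lets ineligibility arising after randomisation end a participant's follow-up, and the eligibility qualifier in 11.2 and 11.4 leaves room to drop randomised participants from the primary analysis

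*Protocol*

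**What the plan says.** Three parts of the protocol bear on this.

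- **Section 9.10 (discontinuation).** It says "the Investigator may discontinue a participant from the trial (or intervention) at any time if the Investigator considers it necessary for any reason", and the first listed reason is "Ineligibility (either arising during the trial or retrospectively". When a participant wishes to stop treatment, the team asks whether follow-up can continue. There is no matching statement for discontinuation by the investigator. The section also says "de-identified data that have already been collected and incorporated in the study database will be included in the analysis", and "No participants will be replaced if they are discontinued or withdraw".
- **Section 11.2 (methods).** The primary analysis "will include all randomised participants for whom data are available, as defined by protocol eligibility". The later sentence on the primary comparison repeats the eligibility qualifier.
- **Section 11.4 (populations).** "The primary analysis population will be all randomised participants, as defined by protocol eligibility criteria, regardless of what intervention they actually received", and the sentence goes on to disregard "compliance of intervention, or completion of outcome". Eligibility is not among the things to be disregarded.

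Section 9.5 adds: "The study is an open label trial". Section 9.4 says that the treatment nurses interact with the experimental arm only.

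**The concern.** An analysis by randomised group needs two things: outcomes sought from everyone randomised, and everyone kept in the comparison. The protocol weakens both.

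First, removal from the trial ends data collection, and 9.10 permits it on the basis of something that happens after allocation. Several exclusion criteria in 8.3 can become true during 26 weeks, among them suicidal ideation with intent, psychiatric in-patient care and other insomnia treatment. The first two are closely tied to a poor depression outcome. A week-26 score lost for such a reason may not be missing at random given the recorded scores.

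Second, if the population were simply everyone randomised, the eligibility qualifier would have no function. Its presence gives an analyst grounds to leave someone out, and it does not say whether eligibility is judged at entry or later, by whom, or with what knowledge of allocation.

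Allocation is known, and the SRT arm has six nurse sessions that TAU does not have. Removal could therefore differ between arms. If it does, and if those removed differ in outcome from those kept, the week-26 PHQ-9 difference is biased.

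**Working it through.** **1. The plan's own figure.** Inputs from 11.3 and 11.7: difference 3 points, SD 6, power 90%, two-sided 5%, attrition 20%, ICC 0.01, cluster size 40. The therapist effect is applied to the SRT arm only.

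- Design effect: 1 + (40 − 1) × 0.01 = 1.39. Optimal allocation ratio: √1.39 = 1.179.
- n(TAU) = (1.39/1.179 + 1) × [(1.960 + 1.282) × 6/3]² = 91.6, rounded up to 92.
- n(SRT) = 1.179 × 91.6 = 108.0, taken as 108.
- After attrition: 92/0.80 = 115 and 108/0.80 = 135, total 250.

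The stated 250 (135/115) is reproduced, with power 90.1% at 108/92. Keeping and following everyone randomised leaves this unchanged. A further 5% loss in both arms would lower power to 88.6%.

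**2. Shift from selective removal.** The protocol gives no removal rates, so everything here is assumed. Let a fraction f of SRT and g of TAU be removed and contribute nothing, and let those removed score D points worse at week 26 than those kept, with D the same in both arms. The mean of those kept is the overall mean minus f × D (or g × D), so

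shift in favour of SRT = (f − g) × D.

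D is taken as 3 to 6 points (0.5 to 1 SD).

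| Removed, SRT / TAU | Shift, D = 3 | Shift, D = 6 | Share of 3-point target |
|---|---|---|---|
| 5% / 5% | 0 | 0 | 0% |
| 5% / 2% | 0.09 | 0.18 | 3–6% |
| 5% / 0% | 0.15 | 0.30 | 5–10% |
| 10% / 2% | 0.24 | 0.48 | 8–16% |
| 2% / 5% | −0.09 | −0.18 | 3–6%, against SRT |

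**3. Effect on the test.** Standard error of the difference: 6 × √(1.39/108 + 1/92) = 0.924. With no true effect, the two-sided error rate rises from 5% to 5.3% at a shift of 0.15, 6.2% at 0.30 and 8.1% at 0.48.

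**4. What the calculation leaves out.** The primary model uses PHQ-9 at weeks 4, 8 and 26 with adjustment for baseline. Someone removed after week 8 whose data are kept still contributes two follow-up scores, which recover part of the gap. The tabulated shifts are therefore upper values for their scenarios. The 10% row is itself a high rate: about 14 of 135 SRT participants (0.10 × 135 = 13.5).

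**The case against.** The strongest reply is that the protocol means eligibility at entry. Section 8.3 words the criteria as conditions for entering the trial, section 7 places no restriction on usual care in either group, 11.4 disregards completion of outcome, and 9.10 keeps data already collected. This stands to a large extent. A reader might infer that participants who become ineligible later leave the primary population; no section says so. What remains is that the qualifier does not say which eligibility it means, and that keeping collected data does nothing for scores never sought.

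A reader might also infer that removal is known to depend on arm and to favour SRT. The documents do not support that. Both arms are asked about unplanned hospitalisations, adverse events and PHQ-9 item 9 at weeks 4, 8 and 26 (10.1 and 10.3), so the events most tied to outcome have a common route of detection. Nurse sessions may add detection in SRT by an unknown amount. Starting another insomnia treatment could be commoner in TAU, which receives no trial sleep treatment, and this would change which arm loses more participants.

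A third tempting reading is that 11.2 (data available) and 11.4 (regardless of completion) define conflicting populations. They can be reconciled: one describes who contributes observations to a mixed model, the other who belongs to the population. That is not part of this point.

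Finally, 11.8 plans sensitivity analyses for missing data, and the SAP, which was not at hand, may sharpen the population. Neither can restore week-26 scores that were not collected because 9.10 ended follow-up.

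**Conclusion.** The point holds as a defect of wording with possible consequences for bias. Permission to end trial participation for ineligibility arising after randomisation, without a provision to continue outcome collection, is explicit in 9.10. The eligibility qualifier in 11.2 and 11.4 is ambiguous and permits exclusion of randomised participants, although it does not direct it. That removal would relate to outcome or differ by arm is a plausible risk, not a documented fact.

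Direction and size are unknown. On assumed removal of up to 10% in one arm against 2% in the other, and an outcome gap of 3 to 6 points, the shift runs from 0 to about 0.5 points against the 3-point target. It is smaller if week-4 and week-8 scores are retained, and zero if removal and outcome gap are equal across arms. The change should be made because it costs little and lost follow-up cannot be repaired at analysis.

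**What to change.** - **Sections 11.2 and 11.4.** Delete the eligibility qualifier wherever it is attached to the primary population or primary comparison. Alternatively, limit it to ineligibility that existed before randomisation, judged from pre-randomisation data by someone blind to allocation, and analyse all others in the arm to which they were randomised.
- **Section 9.10.** State that ineligibility arising after randomisation does not by itself end the scheduled week 4, 8 and 26 outcome collection, unless the participant withdraws from it. Decisions about stopping the intervention are left as they are.

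The cost is wording in three sections. The sample size stays at 250, and no assessments are added beyond those already scheduled.

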Secondary	Mediation hypothesis: To examine if reduction in insomnia at mid- treatment (week 4), drives increased behavioural activation at the end of treatment (week 8), which in turn mediates the treatment effect on depression at follow-up (week 26)	ISI, BADS, PHQ-9	4-,8-, and 26weeks post- randomisation
Secondary	To compare the effect of SRT+TAU versus TAU on self-reported sleep and	Consensus Sleep Diary (CSD) -Sleep diary parameters:	8- and 26-weeks post- randomisation

	daily activation (over 1		
	week)	Sleep onset latency (SOL); Wake-time After Sleep Onset (WASO); Sleep Efficiency (SE); Total Sleep Time (TST); Sleep Quality (SQ); Time in Bed (TIB); Time to bed (TTB); Time out of Bed (TOB) -Level of daily activation computed from evening component of sleep diary	
Secondary	To compare the effect of SRT+TAU versus TAU on psychological well-being	Warwick-Edinburgh Mental Wellbeing Scale (WEMWBS)	8- and 26-weeks post- randomisation
Secondary	To compare the effect of SRT+TAU versus TAU on cognitive complaints	British Columbia Cognitive Complaints Inventory (BC-CCI)	8- and 26-weeks post- randomisation
Secondary	To compare the effect of SRT+TAU versus TAU on pre-defined adverse events	Suicidal ideation (PHQ9 item) and accidents (bespoke questionnaire)	4, 8 and 26- weeks post- randomisation
Tertiary	To compare the effect of SRT+TAU versus TAU on daytime activity levels and light exposure (1 week)	Gross and threshold levels of activity and light exposure quantified from actigraphy and measures of their phase	8- and 26-weeks post- randomisation

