9.4. Randomisation

Following baseline assessments, participants will be eligible for randomisation. Eligible participants will be randomised to SRT+TAU (135 participants) or TAU (115 participants) using a secure, validated and compliant web-based randomisation system (Sortiton), with a non-deterministic minimisation algorithm to ensure practice, use of antidepressant medication (yes/no), current receipt of psychological therapy for depression (yes/no), age (18-65yrs vs. >65yrs), sex (male/female/other), baseline insomnia severity (ISI score: <22 vs. 22-28) and depression severity (PHQ-9 score: <19 vs. 19-27) are balanced across the two groups. Individual randomisation is appropriate because the risk of control group contamination is very low: treatment will be delivered by trained research nurses who will be independent from the practice and will only interact with participants in the experimental arm.

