9.6.2. Description of comparator(s)

Participants randomised to the control group will receive TAU only. It is anticipated that participants receiving TAU will have been prescribed antidepressant medication(s) by their GP and/or have been referred to local IAPT or other psychological therapy services. Usual care for insomnia is likely to be general sleep advice, hypnotics, or sedative antidepressants. We will record TAU in both trial arms.

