10. SAFETY REPORTING

10.1. Serious Adverse Event Definition

A serious adverse event (SAE) is any untoward medical occurrence that:

- results in death
- is life-threatening
- requires inpatient hospitalisation or prolongation of existing hospitalisation
- results in persistent or significant disability/incapacity
- Consists of a congenital anomaly or birth defect.

All participants, and the research nurses facilitating SRT, will be prompted to self-report SAEs. Along with self-reporting of SAEs, we will also ask participants about unplanned hospitalisations (as opposed to elective procedures or planned admissions for treatment) as part of the assessments at 4, 8, and 26 weeks, and follow-up participants who report being hospitalised.

We will record planned hospital admissions at baseline and when they occur, these will not be counted as SAEs. SAEs will be assessed for severity, seriousness, and relatedness to study procedures by a medically qualified member of the team. SAEs will be reported and followed up from date of randomisation until either the date of trial withdrawal or 26-week follow-up completion, whichever is earlier. Any SAEs that are continuing at trial withdrawal or 26-week follow-up completion will be marked as "Continuing" at the end of the study.

Other adverse events that require medical intervention may also be considered a serious adverse event when, based upon appropriate medical judgement, the event may jeopardise the participant and may require medical or surgical intervention to prevent one of the outcomes listed above.

NOTE: The term "life-threatening" in the definition of "serious" refers to an event in which the participant was at risk of death at the time of the event; it does not refer to an event which hypothetically might have caused death if it were more severe.

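### The safety population as defined admits only SRT attenders, so the planned SAE comparison has no TAU group, and limiting the one-session rule to the SRT arm would still drop that arm's non-attenders and their events

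*Protocol*

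**What the plan says.** Protocol section 11.4 defines the set: "The safety population will consist of participants who engaged to some extent (defined as attending at least one session of SRT". Members are then analysed "according to the treatment they actually received (as-treated". The section has no clause on how a TAU participant enters.

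Section 11.2 gives the only SAE test in the protocol: "Numbers of participants who experienced serious adverse events will be compared in the safety population using Chi-square or Fisher's exact test".

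Two other sections settle who can attend SRT. Section 9.6.2 says "Participants randomised to the control group will receive TAU only". Section 9.4 says the nurses who deliver SRT "will only interact with participants in the experimental arm".

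The data are collected more widely than the population allows. Section 10.1 says "All participants, and the research nurses facilitating SRT, will be prompted to self-report SAEs", and SAEs are followed from the date of randomisation to withdrawal or completion of the 26-week follow-up, whichever comes first.

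Section 6 (Table 4) also lists a secondary safety objective: "To compare the effect of SRT+TAU versus TAU on pre-defined adverse events". Neither that table nor section 10.3 names an analysis population for it.

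**The concern.** Sections 11.4 and 11.2 cannot both be followed. The first builds a population from attendance at a treatment that only one arm is offered. The second asks for a between-group test inside it. This goes beyond detail left to the SAP: the protocol states a definition, and that definition defeats a test the protocol also states. An SAP that let TAU participants in would depart from the protocol text.

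At stake is the one formal SAE comparison in a trial of a treatment that deliberately restricts time in bed. If the population is not settled in advance, someone must choose it once events are known, in an open-label trial. The obvious repair, limiting the attendance rule to the SRT arm, has its own problem: it filters one arm by something that happens after randomisation and leaves the other arm whole.

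**Working it through.** **Inputs.** Planned allocation is 135 SRT and 115 TAU (sections 9.4 and 11.3). Entry and grouping rules come from section 11.4, the test from 11.2, control treatment from 9.6.2 and 9.4, and the SAE collection period from 10.1. The protocol gives no size for the safety population, no expected SAE rate and no non-attendance rate.

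**The plan's own figure.** The allocation supplies the denominators below, so it was checked first. With 20% attrition, 135 and 115 become 108 and 92. The design effect in the SRT arm is 1 + (40 − 1) × 0.01 = 1.39. The standard error of the standardised difference is √(1.39/108 + 1/92) = 0.154. Then 0.50/0.154 − 1.96 ≈ 1.285, a power of 0.901 (0.897 with the t distribution), against 90% stated. The sample size reproduces and is not at issue.

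**Reading 1: the definition as written.**

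1. Entry requires at least one SRT session.
2. TAU participants have none by design, so they do not enter.
3. A TAU-randomised participant who somehow attended a session would enter, but as-treated grouping would count that person as SRT.
4. The TAU-received group is therefore empty in every case.

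With *x* SRT participants having an SAE, the table is at most:

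| | SAE | No SAE | Total |
|---|---|---|---|
| SRT | x | 135 − x | 135 |
| TAU | 0 | 0 | 0 |

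- Chi-square: the expected count in each TAU cell is 0 × (column total)/135 = 0. The statistic divides by this, so it is undefined.
- Fisher: with a row total of zero, only one table fits the margins. Hence p = 1 for every *x*, and the odds ratio is undefined. An illustrative x = 5 gave exactly this: odds ratio undefined, p = 1.0, chi-square not computable.

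**Reading 2: the one-session rule applies only to the SRT arm and all TAU participants enter.** The comparison becomes SRT attenders against up to 115 TAU. Let *a* SRT participants attend no session, of whom *e* have an SAE, and let *x* now count attenders with an SAE.

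- SRT risk by randomised arm: (x + e)/135
- SRT risk in attenders: x/(135 − a)
- Difference: (a/135) × [e/a − x/(135 − a)]

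The shift is the non-attendance fraction times the difference in SAE risk between non-attenders and attenders. It is zero if those risks are equal. Because x/(135 − a) is never smaller than x/135, the understatement of SRT risk cannot exceed e/135, that is 1/135 = 0.74 percentage points per excluded participant with an SAE. The protocol supplies neither *a* nor *e*, so the shift cannot be computed.

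The asymmetry itself needs no assumed rate. The SAE clock starts at randomisation, and session 1 comes later. An SRT participant with an SAE in that gap who then never attends is removed together with the event. A TAU participant with an SAE in the same gap is counted.

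**The case against.** **The intent can be recovered.** As-treated grouping and a planned comparison both presuppose two groups. The likeliest explanation is that a clause admitting TAU participants was left out. This stands, and it makes the defect a drafting one. It does not remove it: the protocol nowhere states that clause, and the probable intent leads to Reading 2, which has its own asymmetry.

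**Restricting safety to exposed participants is a common convention.** This also stands. A team may reasonably want an attender set, and including people who never attended may slightly dilute a harm that depends on exposure. That argues for keeping the attender set as a supplement. It does not make it a sound basis for a test between arms when exposure is defined in one arm only.

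**Four stronger readings are tempting and are not supported.**

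- A reader might infer that the adverse-event objective in section 6 also loses its comparator. Section 11.2 ties only the SAE test to the safety population. The pre-defined events are assigned to no population, and section 10.3 speaks of each group when it describes suicidal ideation.
- A reader might infer that as-treated grouping moves SRT non-attenders into TAU and could reverse the direction of the comparison. The one-session rule excludes them before grouping applies. Any numerical reversal would also need non-attendance and SAE rates that the protocol does not give.
- A reader might infer that non-attenders include people already harmed by SRT. They attended no session, and the restriction is introduced in session 1 (Appendix D).
- A reader might say that neither test can be run. Chi-square cannot. Fisher's test can, but its result carries no information.

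The primary efficacy analysis uses all randomised participants and is untouched. Safety stopping guidance is left to the DMC charter, so this point does not bear on it.

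**Conclusion.** The contradiction between sections 11.4 and 11.2 is real and needs correcting. As written, the SAE comparison has 0 of 115 TAU participants, a conclusion that rests on the protocol's own text and no assumed rate. If the attendance rule is limited to the SRT arm, the comparison can be run but treats the arms unequally from randomisation onward. The effect on the SRT risk is at most 0.74 percentage points per excluded event, assuming the planned 135 are randomised to SRT. The total is unknown and could be zero.

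The reach is limited to the SAE test. The pre-defined adverse events have an unassigned population, which should be filled in while the sentence is being changed. No data are lost under either reading. The SAP was not available. If it already handles this, the protocol sentence still has to be brought into line with it.

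**What to change.** In section 11.4, redefine the population for the between-arm SAE comparison as all randomised participants, analysed by randomised arm, counting SAEs from randomisation to withdrawal or 26-week completion, whichever is earlier. This matches the collection period in section 10.1. State that the same population applies to the pre-defined adverse events in sections 6 and 10.3. Keep SRT participants with at least one session as a supplementary, descriptive set without a between-arm test, and carry the same wording into the SAP.

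The cost is a short wording change in section 11.4, matched in the SAP, made before anyone tabulates SAEs by arm. No new data are needed. The one statistical downside is possible slight dilution of an exposure-related harm by SRT participants who attended no session, which the supplementary set addresses.
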